**Participant Consent:** Once the participant contacts the study team through a study flyer, letter, clinical trials database, or provider referral, the study will be explained with an emphasis on the use of random assignment to study groups. The consent process will be completed in a private area of the Bartlett Specialty Practice. To account for low levels of literacy, the study materials have been developed on a 5th grade reading level. Participants will also be given the option to have the consent form read aloud in its entirety. The consent form will be maintained in the study files and participants will be given the option of taking a copy of the signed consent form with them. They will be informed that retention of the form may lead to a breach of confidentiality if the information is shared with someone who does not already know their HIV and/or HCV status.

**Assessment of Protocol Comprehension Prior to Signing Consent:** After the consent form is read by the participant or aloud, the study team member will evaluate comprehension with three protocol-specific questions: 1) What are the problems we are trying to improve?; 2) How does this study plan to improve these problems?; 3) How will you be assigned to the different options in this study? We will deem the participant to have an acceptable level of comprehension based on his/her ability to answer those questions.

**Allocation:** This RCT will be conducted and reported following the CONSORT clinical trial guidelines. The study design is pictured in Figure 1. After recruitment and informed consent, patients will be randomized to the nurse case management intervention group or to the usual care group electronically. Participants will be randomized in a 1:1 fashion using REDCap, a secure online data collection program, to ensure balanced, random assignment to the intervention and usual care groups. REDCap employs a simple randomization technique. This strategy will ensure that the study team has no a priori knowledge of group assignment when enrolling and randomizing study participants.

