After the participant attends the Viral Hepatitis appointment, the research nurse case manager will review the HCV provider's note in the electronic medical record to determine what decision was made about initiating HCV treatment (defer or start). This phase will be single-blinded; no direct communication will occur between the research team and the HCV provider to avoid influencing the HCV management of the patient. The intervention will support the HIV provider and patient without influencing the HCV provider's decisions. Using a Phase 2 Algorithm, the research nurse case manager will identify participants who have a decision to start treatment indicated in the HCV visit note. The anticipated HCV therapy regimen(s) in the clinic note will be assessed for potential drug-drug interactions with the participants' current ART regimen. If a modification in ART is indicated because a contraindicated drug-drug interaction exists, the research nurse case manager will contact the participant via his/her preferred contact method to schedule a follow-up NCM visit. At this visit, the participant will be given a modified one-page drug interaction sheet tailored to his/her ART regimen. The research nurse case manager will also send a secure email to the participant's HIV provider notifying him/her of the potential need for ART modification. This email will include the latest DHHS "Concomitant Use of Selected HIV Drugs and FDA-Approved HCV Drugs for Treatment of HCV in HIV-Infected Adults" table 12. The table will serve as a decision-making aid for the HIV provider to modify the ART regimen if needed. The research nurse case manager will coordinate an ART modification appointment with the participant's primary HIV provider as needed so the patient does not wait the usual 3 to 6 months until his or her next scheduled HIV primary care visit.

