To measure the effectiveness of NCM Phase 2, the electronic medical record will be reviewed 6 months after the enrollment visit. The study team will record whether a change in ART was made during the study period (yes/no). We will also determine if a prescription for HCV therapy was written during the study period, and the time to initiation of that prescribed treatment. The 6-month period for final data collection should be adequate to account for the various steps in HCV treatment preparation among PLWH: 1) linkage to care; 2) ART modification as needed; 3) rechecking the HIV viral load 4 to 8 weeks after modification to ensure viral suppression on new regimen; 4) HCV-related blood tests and imaging, and 5) uncontrollable factors such as appointment cancellations, rescheduling, and reimbursement.

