#### **Study Timeline**

The following 3-year study timeline provides an overview of the study preparation period, enrollment and follow-up (Table 2).

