## 5. Inclusion/Exclusion Criteria

### *Inclusion Criteria*

- HIV infection: This study is examining linkage to HCV care and treatment, with a focus on ART modifications among people living with HIV; therefore, participants must have an HIV diagnosis. People with HIV have a different, accelerated HCV disease course than those with HCV only. People with HIV also have different levels of engagement in healthcare and resources to attend healthcare than the general population due to Ryan White policies. Finally, barriers to engaging in HCV care historically have been different among people with HIV due to particularly low efficacy of HCV treatment options.
- Chronic HCV infection: This study aims to improve linkage to HCV care and treatment in those who need it; therefore, all participants must be chronically infected with HCV. Acute HCV infection is not included in this study because its management and the treatment course are vastly different.
- Age 18+: Most HIV-positive patients at the Bartlett Specialty Practice are over the age of 25 years. Children under the age of 18 years will not be included because management of HCV is different in this population, who does not receive care at the historical Moore Clinic.
- Did not attend appointment with a viral hepatitis provider at Viral Hepatitis Clinic/Bartlett Specialty Practice in past year: The primary goal of this study is to improve linkage to HCV care among those who are not engaged in care; therefore, anyone who has not had a visit at the HCV clinic in the past 1 year will be considered not linked to care because they have not been assessed by an HCV-specific provider in the all-oral era of HCV treatment.
- Ability to speak English: The study team has limited resources to create study materials and provide the nurse case management intervention in multiple languages. The clinic population is primarily African American and Caucasian patients, with few patients speaking no English.
- At least one visit at the Moore HIV Clinic or Bartlett Specialty Practice in the past year: This study aims to test an intervention that can be used in an HIV primary care clinic setting. Participants will be recruited from their regularly scheduled HIV clinic appointments; therefore, those who have been to the clinic in the past year will be considered active clinic patients.

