## 7. Study Statistics

### Analysis:

Data will be cleaned and efforts made to minimize the effects of missing data. All provider visits at Johns Hopkins are registered in the electronic medical record, so absence of a registered appointment during the study period will be considered non-attendance for the primary outcome variable. A computer-based data collection method will be used for data collection of independent variables in attempt to minimize missing data. Exploratory and descriptive analysis will be completed for all study variables. Variables will be tested for normality and examined with means and standard deviations or medians and interquartile ranges accordingly. Baseline characteristics comparing the two groups (usual care vs. intervention) will be assessed. Any differences between the groups will be adjusted for in further analysis. The significance level will be set at 0.05. All tests will be two-tailed and analyzed by intention-to-treat.

**Primary Outcome:** The primary outcome is linkage to care, measured by attendance at the Viral Hepatitis Center (either traditional care or an HCV-treating clinical trial) within 60 days of randomization (yes/no). This hypothesis will be tested using a two-sample z-test for the difference in independent proportions comparing the intervention to usual care groups.

**Secondary Outcome:** The secondary outcome is time to HCV treatment initiation, measured by the number of days from randomization to the date HCV treatment is initiated according to the medical record. Kaplan Meier estimates will be conducted to compare time to HCV treatment initiation between participants in the intervention group and the usual care group, and a log-rank test will be used to test the difference. Covariates (age, sex, race/ethnicity, HCV knowledge, substance use, fibrosis score, CD4+ T cell count, HIV viral load, care giving responsibilities, and participation in Cure Club) will be included in the Cox regression model. To account for a time to treatment initiation greater than the observed time period of 6 months, right censoring will be implemented for participants who have not initiated HCV treatment at the end of the 6-month period.

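### The protocol's own step durations do not support its statement that 6 months is adequate for time to HCV treatment: part of the usual-care pathway with an ART change runs past the censoring date

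*Combined protocol and SAP*

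**What the plan says.** Aim 2 (Section 2) is to shorten the time from randomisation to HCV treatment initiation. Under Phase 2 in Section 4, the record is reviewed 6 months after enrolment, with this justification: "The 6-month period for final data collection should be adequate to account for the various steps in HCV treatment preparation among PLWH". Five steps are listed: linkage, ART modification as needed, a viral load recheck 4 to 8 weeks after the modification, HCV blood tests and imaging, and uncontrollable factors such as rescheduling and reimbursement. Only the recheck is given a duration.

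The same subsection describes what the intervention removes. The nurse arranges an ART modification appointment "so the patient does not wait the usual 3 to 6 months until his or her next scheduled HIV primary care visit". Section 5 adds: "Participants will be recruited from their regularly scheduled HIV clinic appointments".

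Under Secondary Outcome in Section 7, the analysis is Kaplan-Meier, log-rank and Cox, and "right censoring will be implemented for participants who have not initiated HCV treatment at the end of the 6-month period". The Sample Size Justification claims 90% power for a hazard ratio of 2 with 100 participants. It gives neither an event count nor an expected share treated by 6 months.

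**The concern.** Phase 2 is built to remove a wait of 3 to 6 months, yet follow-up ends at 6 months. If a control participant's ART change happens at the next scheduled visit, the recheck, tests and reimbursement still have to follow. Part of that pathway lies beyond the censoring date, mainly in the comparator arm.

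A control who would start on day 200 then looks the same as one who would never start. Section 4 also says that Maryland requires a Metavir score of at least 2 for treatment, so some participants may not be treated through clinical care at all, and the 6-month data cannot tell the two groups apart. A positive result could mean that treatment came earlier, that more people were treated, or both. Starts after the cut-off are also lost as events, while the stated power needs most of the 100 participants to start.

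**Working it through.** **The plan's own figure.** For HR 2, two-sided alpha 0.05 and 90% power, (1.960 + 1.282)² = 10.51.
- Events by Schoenfeld, 1:1: 4 × 10.51 / (ln 2)² = 87.5, so 88.
- Events by Freedman: 10.51 × (3/1)² = 94.6, so 95.
- If all 100 participants start, power is 93.4% (Schoenfeld) or 91.5% (Freedman).

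The stated 90% therefore reproduces only if about 88 to 95 of the 100 start treatment within 6 months.

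**Inputs for the pathway.**
- W, usual wait to the next HIV visit: 3 to 6 months, taken as 90 to 180 days (Section 4, Phase 2).
- V, viral load recheck: 28 to 56 days (same place).
- L, linkage: from 7 days (median to an available new appointment, Patient Population/Setting) to 60 days (the primary outcome window).
- Tests, rescheduling and reimbursement: no figure given; 0, 14 or 30 days assumed.
- Cut-off: day 182.
- Distributions: uniform over each range (assumption).

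**Wait running from enrolment (W + V).** The range is 90 + 28 = 118 to 180 + 56 = 236 days, with mean 135 + 42 = 177. Because 182 − V always lies inside the range of W, the share ready by day 182 is (182 − 42 − 90 − added days) / 90.

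| Days added | Ready by day 182 | Censored first |
|---|---|---|
| 0 | 50/90 = 56% | 44% |
| 14 | 36/90 = 40% | 60% |
| 30 | 20/90 = 22% | 78% |

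**Other clocks.** These use 30.44-day months, so the cut-off is 183 days. Simulated share exceeding 6 months:

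| Clock | Range, no added time | 0 days added | 30 days added |
|---|---|---|---|
| Wait from enrolment | 119 to 239 | 46% | 79% |
| Wait after linkage (L + W + V) | 126 to 299 | 81% | 98% |
| HCV visit at a random point between HIV visits | up to 299 | 22% | 42% |

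**Size within the control arm.** The Sample Size Justification expects 40% of controls to link. The share needing an ART change is put at up to 88%; 30% is assumed as a low value. Per 100 controls, on the enrolment clock:
- Low: 40 × 0.30 × 0.44 = 5.
- High: 40 × 0.88 × 0.78 = 27.

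**Intervention arm.** Study Duration can be read as placing the second nurse visit after day 60. A change at about that time plus the longest recheck gives 60 + 56 = day 116, which leaves 182 − 116 = 66 days for the remaining steps. The squeeze therefore falls mainly on controls.

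**Power.** With HR 2 and 100 participants (Schoenfeld, 1:1), power is 90.8% if 90% start within 6 months, 87.3% if 80% start, 82.6% if 70% start and 68.8% if 50% start. As a favourable case, take 60 linked intervention participants who all start and 40 linked controls who miss the window only through the ART wait. Events are then 100 − 5 = 95 down to 100 − 27 = 73, and power at 40:60 is about 91% down to 82%.

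**Longer follow-up.** On the enrolment clock with 30 days added, the latest path is 180 + 56 + 30 = day 266, inside 9 months (day 274). The after-linkage path reaches day 299, inside 10 months (10 × 30.44 = day 304), but only with no time added for tests.

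**The case against.** The strongest reply is that a common administrative cut-off does not bias Kaplan-Meier curves or the log-rank test. The plan foresees starts after 6 months, specifies censoring for them, and compares timing inside the window validly. This stands. A reader might infer that Aim 2 is invalid or biased, and the documents do not support that. Any finite cut-off also leaves later starts unseen.

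A reader might also infer that the whole usual-care pathway exceeds 6 months. It does not: the lower end (118 to 126 days) fits, the enrolment-clock mean of 177 days is just inside, and participants who need no ART change skip the long step. The 3 to 6 months is the usual wait to the next scheduled visit; nothing says that every control waits for it. Section 8 says that the HCV or HIV provider would raise the change regardless of the study. Recruitment in Section 4 also allows entry through flyers, letters, trial listings and calls, so day 0 need not be an HIV visit. That is why the 44% is conditional and the 22% to 81% range is shown.

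Two further inferences fail. Year 3 of Table 2 is headed Follow-Up and is not shown to be unused; 6-month reviews already run to month 30 if enrolment ends at month 24. And 9 months does not cover every path. What the reply does not rescue is the unqualified claim of adequacy: a 6-month wait plus the shortest recheck (180 + 28 = day 208) already overruns, before tests, imaging or reimbursement.

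**Conclusion.** The concern holds in a limited form. The statement that 6 months is adequate conflicts with the protocol's own durations for linked usual-care participants who need an ART change and have it at the next scheduled visit. Of these, 44% to 78% would be censored before they could start on the enrolment clock with 0 to 30 days added, and 22% to 81% across clocks with no added time. The figures rest on uniform distributions, and the documents give neither the actual share needing a change nor the time for tests and reimbursement. That many controls overall would be affected is plausible but not established.

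The 6-month comparison answers whether treatment starts within 6 months. It cannot show whether controls catch up afterwards, which limits a conclusion of decreased time. This is a secondary outcome; the change should be made, but the primary analysis is not touched.

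**What to change.** In Section 4 (Phase 2, Study Duration and Table 1) and in Section 7 (Secondary Outcome):

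- Move the treatment-initiation record review and the censoring date to at least 9 months after randomisation, or about 10 months to cover the longest path in the stated figures.
- Keep the 6-month proportion treated as an intermediate summary, and leave the exit interview at 6 months.
- Remove the adequacy statement, or qualify it with a duration for each of the five steps.
- State the expected share treated in each arm by the cut-off, and restate power in events.

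If follow-up is not extended, restate Aim 2 as treatment initiation within 6 months of randomisation.

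By the column headings of Table 2, enrolment ends by month 24, so the last review falls at month 33 or 34, within Year 3. The cost is a protocol, consent and privacy-authorisation amendment and a final analysis 3 to 4 months later, which leaves 2 to 3 months of the 3-year plan for analysis and reporting. Because the outcome is abstracted from the record, no visit, procedure or participant is added.

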**Table 1. Nurse Case Management Intervention and Study Visit Schedule**

|  | Enrollment | Before HCV appt. | HCV appt. | NCM visit | ART change appt. a | 6 months |
|--|------------|------------------|-----------|-----------|-------------------------------|----------|
| Administrative and Data Collection Procedures |            |                  |           |           |                               |          |
| Informed Consent                                     | X          |                  |           |           |                               |          |
| Baseline questionnaire                               | X          |                  |           |           |                               |          |
| Randomization  | X          |                  |           |           |                               |          |
| Medical record abstraction: Linkage to care          |            |                  | X         |           |                               |          |
| Medical record abstraction: Treatment initiation     |            |                  |           |           |                               | X        |
| Exit Interview                                       |            |                  |           |           |                               | X        |

Date: May 8, 2017

Principal Investigator: [name], MPH, NP

Application Number: IRB00081068

| NCM Phase 1: Linking to Care                              |   |                |   |   |   |  |
|---|---|----------------|---|---|---|--|
| Nurse-initiated Referral                                  | I |                |   |   |   |  |
| Strengths-Based Education        | I |                |   |   |   |  |
| Patient Navigation                     | I | I b |   |   |   |  |
| Appointment Reminders                     |   | I c |   |   |   |  |
| NCM Phase 2: Treatment Initiation d            |   |                |   |   |   |  |
| Care Coordination of ART Modification  |   |                | I | I | I |  |

X=all participants; I=intervention arm only; appt.= appointment; NCM=nurse case management; aART change appointment with HIV provider; bParticipants will be encouraged to call the research nurse case manager for needs relating to linking to HCV care and initiating HCV treatment; cAppointment reminders will occur 1 day and 1 week (if applicable) before HCV appointment; dIncludes participants from Phase 1 who link to an HCV provider only

#### **Exit Interview (Intervention and Control Participants):**

At the time of the 6-month medical record review to evaluate the study outcomes, participants in both groups will be called by a study team member other than the research nurse case manager to complete an exit interview. The purpose of this interview is to identify barriers that participants in both groups encountered in linking to HCV care and initiating therapy during the study period, as well as to measure the intervention group's perception of the content, quality, and quantity of the intervention delivered by the research nurse case manager. This interview will also help to explain the acceptability and of the intervention as well as its success or failure among patients in the intervention group.

Participants will be asked to answer a short survey with the opportunity to provide an open-ended response to explain their answer or give additional feedback about the intervention and participation in the study. A separate survey will be given to the control and intervention groups. The Nurse Case Management group will be asked about overall feedback about participation in the study, barriers to linking to HCV care and treatment initiation, and evaluation of the interventionist. The Enhanced Usual Care group will receive the same questions about overall feedback and barriers, but without the evaluation of the interventionist questions, so that comparisons can be made between the two groups about satisfaction with participation in the study and barriers to linking to and engaging in HCV care.

#### **Study Timeline**

The following 3-year study timeline provides an overview of the study preparation period, enrollment and follow-up (Table 2).

**Table 2: Timeline**

| Year                                   | First 6 months | Second 6 months | Year 2     | Year 3    |
|--|----------------|-----------------|------------|-----------|
| Task                                   | Preparation    | Enrollment      | Enrollment | Follow-Up |
| IRB Process                            |                |                 |            |           |
| Identify/Train Research Assistants     |                |                 |            |           |
| Recruitment/Informed Consent/Screening |                |                 |            |           |
| NCM Intervention and Study Visits      |                |                 |            |           |
| Medical Record Review of Outcomes      |                |                 |            |           |

Date: May 8, 2017

Principal Investigator: [name], MPH, NP

Application Number: IRB00081068

|                                      |  |  |  |  |
|--------------------------------------|--|--|--|--|
| Data Entry and Statistical Analysis  |  |  |  |  |
| Present at Meetings and Publish Data |  |  |  |  |

**Study Duration:** Final data collection for each participant will occur 6 months after the date of enrollment (Table 1). Participants will be asked to complete a maximum of two study visits. Participants in both groups will have a baseline study visit consisting of informed consent, baseline questionnaire, and medical record review. Participants in the enhanced usual care group will receive the CDC HCV Fact Sheet at this time and require no further follow-up visits. Participants in the NCM intervention group will receive intervention Phase 1 at the time of the baseline visit. A second visit will occur for participants in the intervention group who are included in Phase 2 after 60 days to coordinate ART modifications with the nurse case manager, as described under Phase 2 – Treatment Initiation above. After 6 months, the study team will review the medical record for final data collection. Participants will be contacted via their preferred method at 6 months to respond to an exit survey, which may take place over the phone.

